Contrary to what some of these studies suggest, it has been our experience that nasal intubations using the C-Mac frequently do not require the use of Magill forceps at nearly the same rate as DL additionally they may overall be easier. As a result, this technique may improve the over all time and ease of intubation because of not having to use the Magill forceps to advance the Nasal RAE into the larynx. The use of Magill forceps can be awkward for the clinician, with poor visualization due to obstruction of the view by this tool in the airway, and small working space within the posterior oropharynx. For these reasons, the possibility of not having to use Magill forceps because we are using a C-Mac as the only tool to intubate is a potentially inviting one. Overall there may be other positive effects to having a closer and more magnified view of the glottis as well.

Objectives

The objective of this study is to compare the need for the use of standard Magill forceps when performing a nasal intubation with either conventional DL or VL with a C-Mac and overall ease of intubation. Secondly we will also examine the time to intubate (TTI) for both methods as well.

An additional objective will be to assess if there are any other significant clinical differences between these two approaches to placement i.e. increased rates of overall failure, clinical morbidity such as laryngeal or pharyngeal injury.

Methods and Measures

Design

Once the patient is recruited in the pre-admission clinic (PAC), this information will be relayed to the study investigators. On the day of surgery, the patient will then be randomized using a random number generator and opaque envelope method for group allocation to either DL or VL with a C-Mac. In a minority of cases where a suitable patient has not gone through the PAC we will attempt to recruit them prior to going to the operating room after the pre-anesthetic evaluation.

We will record age, height, weight, gender, ASA status.

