The patient will be pre-medicated at the discretion of the attending anesthesiologist. The patient will then be randomized to either DL or VL with a C-Mac. The patient will be brought to the operating room. Once in the OR the patient will have routine monitors placed. The patient will undergo an inhalational induction with sevoflurane. Once anesthesia has been induced, an IV will be placed. The patient will be relaxed with 0.8 mg/kg of rocuronium IV. The patient will then be hand-ventilated with 100% oxygen and sevoflurane for 3 minutes to allow for adequate relaxation and an end tidal oxygen concentration of at least 80%. During this time, the patient will receive oxymetolazine in both nares to reduce the risk of bleeding with a nasal tube. Prior to intubation, we will also attempt to insert an appropriately sized flexible nasal trumpet to assess which nares provides the least resistance to passage of an ETT. After 3 minutes have elapsed since the administration of rocuronium, an appropriately sized cuffed nasal RAE ETT that has been warmed using a warm blanket, and then lubricated with a water soluble lubricant will be inserted into the nares. Once the ETT is passed into the posterior oropharynx, depending on which randomized group the patient has been assigned (VL or DL), an attending pediatric anesthesiologist or a pediatric Certified Registered Nurse Anesthetist (CRNA) who has experience performing nasal intubations with both DL and with the C-Mac will attempt to intubate the patient with or without Magill forceps as needed.

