We will record the time to intubation (TTI) from the time the laryngoscope or C-Mac is placed in the mouth to the first appearance of end tidal carbon dioxide (ETCO₂). We will record the presence or absence of nasal bleeding and its level of severity using a 4 point scale (0 No bleeding, 1-Trace, 2-Moderate, 3-copious) as well as the grade of laryngeal view. We will record the number of attempts. If the blade is removed from the mouth this will be considered the end of one attempt, and once the blade is reinserted this will be the beginning of another attempt. We will also record any general narrative comments from practitioners about the ease or difficulty of intubation in both the DL and VL group. In addition to the narrative comments we will have the laryngoscopist grade the degree of difficulty on a 100mm VAS scale after the intubation (0 easiest -100 most difficult). The laryngoscopist will be blinded to TTI until VAS score and other airway data are recorded. Intubation will be considered a failure at 5 minutes. At this point it will be at the discretion of the anesthesiologist of record to decide how to proceed, either with an oral tube or different technique for nasal intubation. TTI will be considered 5 minutes for the purposes of analysis and device comparison. We will record the lowest SpO₂ during intubation.

The patient will be extubated according to normal clinical practices and will be taken to the post anesthesia care unit (PACU).

Patients will be observed in the PACU and any significant events such as unintended admission, excessive hoarseness, persistent nasal bleeding, or pharyngeal injury will be recorded.

The study will be performed at Wake Forest Baptist Medical Center a tertiary academic medical center.

C-Mac Product Information

The C-Mac Video laryngoscope is produced by Karl Storz products. Product specifications can be found at:

https://www.karlstorz.com/cps/rde/xber/karlstorz_assets/ASSETS/3436753.pdf

<http://www.airwayworld.com/wp-content/uploads/2013/08/1.-C-MAC-VIDEO-LARYNGOSCOPES.pdf>

<http://www.airwayworld.com/wp-content/uploads/2013/08/Neonate-Pediatrics.pdf>

Subjects selection criteria

Pediatric patients between the ages of 3 and 14 scheduled for comprehensive dental treatment in which a nasal tube would be an appropriate method to secure of the airway.

- **Inclusion Criteria**

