Patients between the ages of 3 and 14 scheduled for comprehensive dental treatment, tooth extraction, or incision and drainage of tooth abscess under general anesthesia in which a nasal endotracheal tube is an appropriate method for securing the airway.
Normal appearing airway upon pre-operative assessment.

- **Exclusion Criteria**

Patient with a history of difficult airway/intubation
Patients suspected to have a difficult airway.
History of cleft palate and/or cleft palate repair
Pregnancy
Emergency status of surgery
Any patient with a contra-indication to nasal tube placement
Any patient with a potentially increased risk of nasal bleeding from nasal placement of the ETT i.e. patients on aspirin or other anticoagulants, patient's with hemophilia,

- **Sample Size**

Based on a published rate of approximately 90% of patients requiring Magill forceps to place a Nasal RAE ETT with DL and a rate of 50% based on pilot data in patients with a C-Mac VL system, we have performed a power calculation to determine the sample size needed. Based on a power of 80% and an alpha of 1% we have calculated a sample size of 35 patients in each group to be able to detect a significant difference in the rate of use of Magill forceps to place a nasal RAE ETT in this patient population. This is not a multi-site study.

Interventions and Interactions

Interventions and interactions for the patient should be fairly reasonable. The largest overall commitment of time from the patient will be in the PAC or preoperatively in holding at the time of recruitment. One of the PAC investigators interview the patient's legal guardian (frequently their parents) and the patient for assent when appropriate. They will explain the study and attempt to recruit the patient if they are eligible. The study participant and their guardian will have their questions answered and if they agree to allow their child to participate will sign the consent form. Assent will be obtained from cognitively intact children over the age of 7.

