In patients that have gone through and been recruited in the PAC, the patient will be identified in the holding area on the day of surgery and a study representative will make sure that the guardian or patient has not changed their mind about participation and will answer any questions the study subject may have thought of since the interview in PAC. If the patient's guardian is still in agreement to participate in the study they will be taken to the OR and care will proceed as it would otherwise with the induction of general anesthesia and attempted placement of a nasal RAE ETT via DL or VL with a C-Mac depending on which randomization group to which the patient has been randomized. After the procedure, the patient

will be observed in the PACU and discharged to home. A study representative will thank them for their participation and this will be the last interaction with the patient and patient’s guardian in the study.

	Patient identified in PAC.	Patient approached in PAC and questions answered about. Patient to sign consent for study participation here.	Confirmation and randomization on day of surgery	Patient intubated after induction of anesthesia. Data collected about nasal intubation including time to intubate and laryngeal view.	Patient will undergo dental procedure.	At the end of the dental procedure. The ETT will be removed and the patient will be taken to PACU	Patient will be observed and recovered post operatively in the PACU. Any significantly airway injuries or recurrent nasal bleeding will be noted.
Time required of Patient	0 min	20 min	5 min	10 min	Depends on surgical duration.	5 minutes	5-10 min

Outcome Measure(s)

We will record time to intubate and will assess the need for Magill forceps for intubation. We will also record grade of larynx view, presence of nasal bleeding, any and all comments from the practitioner related to intubation, and incidence of failed nasal intubation.

Analytical Plan

Results will be analyzed initially using descriptive statistics. Comparison between the two groups will be done using Fisher’s Test, and ANOVA procedures for continuous variables. Other inferential statistical analysis will be conducted as appropriate.

Human Subjects Protection

Subject Recruitment Methods

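### The objective is the need for Magill forceps but the sizing outcome is their use, which an unblinded operator decides, so a difference in use can partly reflect habit or expectation

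*Combined protocol and SAP*

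**What the plan says.** Two words are used for one outcome. Under Objectives the trial is to "compare the need for the use of standard Magill forceps when performing a nasal intubation" by DL or with the C-Mac, and Outcome Measure(s) says the team "will assess the need for Magill forceps for intubation". Sample Size instead refers to "a significant difference in the rate of use of Magill forceps to place a nasal RAE ETT". It takes 90% for DL from a published rate and 50% for the C-Mac from pilot data, with 80% power, alpha 1% and 35 children per group. No outcome is labelled primary; this is the only one used for sizing.

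The only text on how forceps come to be used is in Methods and Measures, Design. The operator "will attempt to intubate the patient with or without Magill forceps as needed", and is someone "who has experience performing nasal intubations with both DL and with the C-Mac". The same section states one blinding measure: "The laryngoscopist will be blinded to TTI until VAS score and other airway data are recorded" (TTI is time to intubation). Under Background, Rationale and Context the team gives its expectation: "it has been our experience that nasal intubations using the C-Mac frequently do not require the use of Magill forceps". That sentence continues as a comparison with DL, so it claims a lower rate than DL and not a low rate outright.

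**The concern.** Need is a property of the child, the tube and the view. Use is a decision. The two agree only if operators take up forceps on the same grounds in both arms, and the protocol neither states those grounds nor asks for them to be recorded. An operator could reach for forceps sooner with DL, or persist longer without them with the C-Mac, and either would count as a valid outcome.

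Randomisation does not protect against this, because it arises after allocation, in the unblinded decision that is itself the endpoint. Blinding the operator to TTI does not bear on that decision. The opaque envelopes, the operators' experience, the definition of an attempt and the 5-minute failure limit do not govern it either.

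What is at stake is the wording of the main conclusion. A significant result would be a sound statement about use under these operators. It would not by itself show that the C-Mac reduces the need for forceps.

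**Working it through.** **Inputs.** From Sample Size: DL 90%, C-Mac 50%, alpha 1%, power 80%, 35 per group. From Analytical Plan: Fisher's test. Sidedness is not stated; two-sided is assumed.

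**The plan's own figure.** With p1 = 0.9, p2 = 0.5, mean 0.7 and difference d = 0.4, the pooled two-sided formula gives

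n = [2.576·√(2·0.7·0.3) + 0.842·√(0.9·0.1 + 0.5·0.5)]² / 0.4² = (1.669 + 0.491)² / 0.16 ≈ 29.2, so 30.

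The continuity correction gives n' = (n/4)·[1 + √(1 + 4/(n·d))]² = (29.16/4)·[1 + √1.343]² ≈ 34.0, so 34. The stated 35 is reproduced to within one patient. Exact power of the two-sided Fisher test at 35 per group is 84.4%. The sample-size arithmetic is not at issue.

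**Illustration of the shift.** The documents give no figure for operator discretion, so every shift below is an assumption. The probability of a significant result is

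P = Σᵢ Σⱼ Bin(i; 35, p_DL) · Bin(j; 35, p_CMac) · 1[Fisher p(i, j) ≤ 0.01].

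Scenario A: true need is 50% in both arms. With DL, forceps are also used in a share e of the children who did not need them; with the C-Mac this never happens. Recorded DL use is 0.5 + 0.5e.

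| e | Recorded DL use | Recorded C-Mac use | P(significant) |
|---|---|---|---|
| 0 | 50% | 50% | 0.6% |
| 0.2 | 60% | 50% | 2.6% |
| 0.4 | 70% | 50% | 13% |
| 0.6 | 80% | 50% | 43% |

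Scenario B: true need is 90% in both arms, and discretion lowers recorded C-Mac use.

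| Points lower | Recorded DL use | Recorded C-Mac use | P(significant) |
|---|---|---|---|
| 0 | 90% | 90% | 0.1% |
| 10 | 90% | 80% | 3.4% |
| 20 | 90% | 70% | 22% |
| 30 | 90% | 60% | 56% |

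In both scenarios a 10-point shift already exceeds the nominal 1%, read as a test of need.

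**Sensitivity of a borderline result.** With 32/35 DL children given forceps, the result is significant at 1% when the C-Mac count is 22/35 or lower. With 31/35, the C-Mac count must be 20/35 or lower. So if 32 against 22 is observed, rescoring one DL child as not needing forceps (and no C-Mac child) gives 31 against 22, which is no longer significant.

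**The case against.** Use as needed is a legitimate pragmatic outcome, and a known device does not by itself produce a large gap: the paediatric study of another video device cited in the Background found forceps used in 90% with DL and 87.5% with video. The Background also describes DL as guiding the tube first and bringing in forceps when required, which does not fit a habit of reaching for them at once. Long persistence without forceps with the C-Mac would tend to show in TTI, and difficulty in the number of attempts, the visual analogue score or the narrative comments. The data collection form is listed in the Appendix but not available here, so it may already hold a criterion or a reason field.

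Much of this stands. The Background passage is description and not a rule of the trial, and the other measures are partial checks: none records why forceps were taken up. The form should be checked before anything is added.

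Three stronger readings do not hold. A reader might infer that the team regards forceps as rarely required with the C-Mac; the text claims only a lower rate than DL, and the planned C-Mac rate is 50%. A reader might infer that habit could account for the whole planned 90% against 50%. In scenario A that needs e = 0.8 (0.5 + 0.5·0.8 = 0.9; P = 84%) and no unneeded use with the C-Mac, and the documents support neither. A reader might also infer that the protocol must fix an intubation sequence before forceps are allowed. That is a clinical matter for the sponsor. Rescoring the main outcome as need could also lower the DL rate: at 80% against 50%, power with 35 per group is 43%, so the sample size would have to be revisited.

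**Conclusion.** The concern holds as a risk to interpretation. The documents name *need* as the target and size on *use*, with an unblinded operator, a stated expectation and no record of the basis for the decision. Followed as written, the available text does not let a reader separate a device effect from operator choice. The documents do not show that such bias occurs, or how large it would be. The illustrative chances of 2.6%, 13% and 43%, against 0.6%, rest on equal true need of 50%, discretion acting in the DL arm only, and a two-sided test. The sample size stands. The correction is worth making before enrolment, because the reason for taking up forceps cannot be reliably recovered afterwards.

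**What to change.** Reconcile the two words without prescribing technique.

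- Keep forceps use (yes/no) as the sizing outcome, so that the 90% and 50% assumptions and 35 per group stand, and state the main conclusion as use.
- For every child in both arms, record whether passage without forceps was tried before they were taken up, and the reason for taking them up. First confirm whether the data collection form already has these fields. The operator remains free to use forceps at any time.
- Report by arm the number of children in whom forceps were taken up without a prior try.
- Prespecify a sensitivity analysis that scores those children first as needing and then as not needing forceps. Claim a reduction in need only if the result holds under both.

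The cost is two or three data fields, a little more analysis and possibly a more limited conclusion. It needs no extra patients, since the sizing outcome is unchanged. The operator still judges the reason. The bias from early take-up is therefore made visible and bounded, not removed, and unequal persistence without forceps would still have to be looked for in TTI and attempts.

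### Nasal bleeding is graded 0-3 but listed as an outcome only by its presence, and no ordered comparison is committed to for bleeding grade or laryngeal view

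*Combined protocol and SAP*

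**What the plan says.** Under Methods and Measures, Design, the protocol records whether there is nasal bleeding and "its level of severity using a 4 point scale (0 No bleeding, 1-Trace, 2-Moderate, 3-copious". The same sentence adds laryngeal view: "as well as the grade of laryngeal view". The scale for laryngeal view is not given.

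Outcome Measure(s) then lists: "We will also record grade of larynx view, presence of nasal bleeding". Laryngeal view keeps its grade there. Bleeding appears only as presence.

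The Analytical Plan starts with descriptive statistics. It then names Fisher's test and "ANOVA procedures for continuous variables", and closes by allowing other inferential analyses where suitable. No rank, trend or proportional-odds method is named for any outcome.

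The Sample Size section concerns Magill forceps use alone. Nothing is powered for bleeding or laryngeal view.

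**The concern.** The two sections do not agree on what the bleeding outcome is. Neither graded outcome is continuous, so Fisher's test is the only named method left for them, and it takes no account of order. A reader who pairs the listed outcome with the named test would compare any bleeding with none, and a trace would weigh as much as copious bleeding. A null result on presence could then be reported as no difference in bleeding, although the grades recorded for the same children pointed the other way.

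The open clause also leaves the choice between presence and grade, and the choice of test, until the data are in hand. The laryngoscopist knows the device and is blinded only to time to intubation, so it is better to settle that choice beforehand.

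**Working it through.** **1. The plan's own figure.** Inputs from Sample Size: 90% forceps use with direct laryngoscopy, 50% with the C-Mac, power 80%, alpha 1%, and "we have calculated a sample size of 35 patients in each group". Two-sided, with mean rate 0.70:

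n = [2.576·√(2·0.70·0.30) + 0.842·√(0.09 + 0.25)]² / 0.40² = (1.669 + 0.491)² / 0.16 ≈ 29.2, so 30 per group.

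With continuity correction: (29.2/4)·[1 + √(1 + 4/(29.2·0.40))]² ≈ 34. The stated 35 is reproduced to within one patient. Exact power of Fisher's test at 35 per group and alpha 1% is 84.4%. This figure does not bear on bleeding, but it fixes the arm size used below.

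**2. Assumptions.** The documents give no bleeding distribution, no expected effect and no significance level for secondary outcomes. I assume two reference distributions over grades 0/1/2/3 (55/25/15/5% and 30/40/22/8%), a common odds ratio of 3, and two-sided 5%.

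**3. The shift.** Under proportional odds, each cumulative odds c/(1 − c) is divided by 3 for more bleeding or multiplied by 3 for less. For no bleeding:
- 55% is odds 1.222. Divided by 3 this is 0.407, or 28.9%; multiplied by 3 it is 3.667, or 78.6%.
- 30% is odds 0.429. Divided by 3 this is 0.143, or 12.5%; multiplied by 3 it is 1.286, or 56.3%.

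**4. Power at 35 per arm.** The binary tests are evaluated by summing binomial probabilities over all tables. The tie-corrected Wilcoxon test is simulated.

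| Reference arm | Shift | Fisher, presence | Uncorrected chi-square, presence | Wilcoxon, grade |
|---|---|---|---|---|
| 55/25/15/5 | more | 50% | 59% | 69% |
| 30/40/22/8 | more | 33% | 43% | 70% |
| 55/25/15/5 | less | 47% | 57% | 57% |
| 30/40/22/8 | less | 50% | 59% | 68% |

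(Simulating Fisher in the last row gives 50 to 51%; the exact value is 50.3%.)

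The total gaps are 19, 37, 10 and 18 points. Of these, 9 to 10 points in each row come from Fisher's conservatism: its rejection rate under no difference is 2.5 to 2.8%, against about 5% for Wilcoxon. Discarding the grades accounts for the rest, from nothing in the third row to about 27 points in the second.

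**5. Other distributions.** With reference arms 40/35/20/5, 60/25/12/3 and 25/35/30/10, a shift toward less bleeding and odds ratios of 2 to 4, the ordered test gains about 7 to 20 points over Fisher on presence. Against a normal-approximation binary test the gain is about 1 to 11 points.

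**6. Keeping grades but ignoring order.** At odds ratio 3 for those three distributions, an unordered 2×4 chi-square has 47%, 35% and 51% power, against 65%, 53% and 70% for the ordered test. This bears on laryngeal view as well, with the caution that its number of grades is not stated.

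**7. Severity shifts, presence does not.** Suppose 60% bleed in both arms, with moderate or copious bleeding in 10% v 40%. Fisher on presence has 3% power, Wilcoxon about 29%, and Fisher on grade 2 or above 78%. A rank test alone is therefore not a full remedy.

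**The case against.** The best reply is that the plan is loose here, not wrong. Outcome Measure(s) reads as a summary: it also leaves out the difficulty score, the number of attempts and the lowest oxygen saturation, all recorded under Design. Presence may be shorthand. Descriptive statistics come first and would normally show counts per grade, and the closing clause allows an ordered test. All of that stands, and it limits the point to a missing commitment.

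Three stronger readings are tempting, and the documents do not support them.
- *Severity information is lost.* It is not: Design requires the grade to be recorded. What is missing is a stated analysis of it.
- *Laryngeal view will be compared by a test that ignores order.* No test is assigned to it, and it stays a grade in the outcome list. Its only gap is the absence of a named ordered method.
- *Bleeding is the trial's main harm outcome.* Objectives names failure and laryngeal or pharyngeal injury as examples, not bleeding. In both arms the nasal trumpet attempt and passage of the tube through the nose come before the randomised device is used, so part of the bleeding exposure precedes the comparison.

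It is also fair to object that the power gain depends on direction and distribution, that some of it would come from any less conservative binary test, and that Wilcoxon performs poorly when only severity changes. These objections are right. They are why both directions are shown above and why the fix does not rest on a rank test alone.

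**Conclusion.** The point holds in limited form. The sections on Design and Outcome Measure(s) disagree on whether bleeding is a 0-3 grade or a yes/no outcome, and no ordered analysis is pre-specified for either graded outcome. If the listed outcome is analysed by the named test, the loss at 35 per arm is roughly 10 to 37 points of power at an odds ratio of 3 under the two main assumed distributions. About 9 to 10 of those points reflect Fisher's conservatism, not the reduction to presence. The direction of the loss is consistent across the scenarios, but its size cannot be derived from the documents.

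The consequence is confined to unpowered secondary outcomes. It should not be read as a flaw in the comparison of Magill forceps use or its sample size.

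**What to change.** In Outcome Measure(s), replace presence of nasal bleeding with *nasal bleeding grade (0-3)*, in line with Design.

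In the Analytical Plan, state that:
- bleeding grade and laryngeal view grade are each compared by a Wilcoxon rank-sum test or a proportional-odds model, choosing one in advance;
- counts per grade are reported by arm;
- the proportion with moderate or copious bleeding (grade 2 or above) is reported by arm, with a confidence interval for the difference.

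The last item covers the case where severity shifts but presence does not, in which a rank test is weak and a common odds ratio would be a poor summary. Presence can stay as a descriptive line.

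The cost is a few sentences and a small amount of extra analysis. Both grades are already to be recorded, so no new data, patients or procedures are needed, and the 35 per group is unchanged.
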